10.2 Reporting Period

Details of all AEs (except those listed above) will be documented and reported from the date that the patient is consented into the trial until 28 days after the administration of the last dose of trial medication.

SAEs that are judged to be at least possibly related to trial treatment must still be reported in an expedited manner irrespective of how long after IMP administration the reaction occurred.

STOMP Protocol

10.3 Reporting procedure

10.3.1 Site

10.3.1.1 Adverse Events

AEs should be reported on an AE Form (and where applicable on an SAE Form). An AE Form should be completed at each visit and returned to the STOMP Trial Office.

AEs will be reviewed using the CTCAE, version 4.0 (see Appendix 5). Any AEs experienced by the patient but not included in the CTCAE should be graded by an Investigator and recorded on the AE Form using a scale of (1) mild, (2) moderate or (3) severe. For each sign/symptom, the highest grade observed since the last visit should be recorded.

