10.3.1.2 Serious Adverse Events

For more detailed instructions on SAE reporting refer to the SAE Form Completion Guidelines contained in section 5.0 of the ISF.

AEs defined as serious and which require reporting as an SAE should be reported on an SAE Form. When completing the form, the Investigator will be asked to define the causality and the severity of the AE which should be documented using the CTCAE version 4.0.

On becoming aware that a patient has experienced an SAE, the Investigator (or delegate) must complete, date and sign an SAE Form. The form should be faxed together with a SAE Fax Cover Sheet to the Trial Office using one of the numbers listed below as soon as possible and no later than 24 hours after first becoming aware of the event:

To report an SAE, fax the SAE Form with an SAE Fax Cover Sheet to:

[name] or [name]

On receipt the STOMP Trial Office will allocate each SAE a unique reference number. This number will be transcribed onto the SAE Fax Cover Sheet which will then be faxed back to the site as proof of receipt. If confirmation of receipt is not received within 1 working day please contact the Trial Office. The SAE reference number should be quoted on all correspondence and follow-up reports regarding the SAE. The SAE Fax Cover Sheet completed by the Trial Office should be filed with the SAE Form in the ISF.

For SAE Forms completed by someone other than the Investigator the Investigator will be required to countersign the original SAE Form to confirm agreement with the causality and severity assessments. The form should then be returned to the Trial Office in the post and a copy kept in the ISF.

Investigators should also report SAEs to their own Trust in accordance with local practice.

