15.2 Definition of secondary outcome measures

Overall survival time is defined as the interval in whole days between the date of randomisation into the trial and date of death from any cause. Patients who do not die during the course of the trial will be censored at the date when they were last known to be alive. The median survival will be reported as will the six month survival rate, both of which will be calculated using the method of Kaplan-Meier estimation.

Performance status of the patient is classified by the clinician at each treatment visit according to ECOG definitions (Oken *et al.*, 1982). The trial will assess the change over time in this measure.

AEs will be recorded according to the definitions given in Appendix 4 of the protocol with grade of events recorded by CTCAE version 4.0. Treatments will specifically be compared in terms of the number of patients who experience at least one grade 3 or grade 4 AE.

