15.4 Methods for analysis

All analyses will be carried out on an intention-to-treat basis. Median progression-free survival time and overall survival time will be reported using Kaplan-Meier estimates together with 90% confidence intervals. In addition the survival rates at 4 and 6 months will be estimated and provided with 90% confidence intervals. Progression-free survival will be compared for each treatment arm to the pooled control group using the log-rank test.

In addition to the log-rank test, analysis of PFS using a Cox proportional hazards model will be considered. This analysis of PFS will adjust for prognostic factors in addition to the trial stratification factors. These factors may include stage and performance status at diagnosis. Consideration will also be given to the use of an interval censored data approach to the analysis of PFS.

Once 105 PFS events have been observed then there will also be an interim assessment of overall survival. A further analysis of overall survival will be performed after a further 6 months of follow up.

Changes in performance status over time will be assessed using longitudinal methods of analysis and will account for informative dropout. AEs, as a whole, will be reported as the number of patients on each treatment arm experiencing each event at each grade. In particular, the difference in the number of patients experiencing at least one grade 3 or grade 4 AE will be estimated with a 95% confidence interval.

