APPENDIX 4- DEFINITION OF ADVERSE EVENTS

Adverse Event

Any untoward medical occurrence in a patient or clinical trial subject administered a medicinal product and which does not necessarily have a causal relationship with this treatment.

Comment:

An AE can therefore be any unfavourable and unintended sign (including abnormal laboratory findings), symptom or disease temporally associated with the use of an IMP, whether or not related to the IMP.

Adverse Reaction

All untoward and unintended responses to an IMP related to any dose administered.

Comment:

An AE judged by either the reporting Investigator or Sponsor as having causal relationship to the IMP qualifies as an Adverse Reaction (AR). The expression reasonable causal relationship means to convey in general that there is evidence or argument to suggest a causal relationship.

Serious Adverse Event

Any untoward medical occurrence or effect that at any dose:

- Results in death (unrelated to original cancer)
- Is life-threatening*
- Requires hospitalisation** or prolongation of existing inpatients' hospitalisation
- Results in persistent or significant disability or incapacity
- Is a congenital anomaly/birth defect
- Or is otherwise considered medically significant by the Investigator***

For the purposes of the STOMP trial development of MDS/AML is considered significant and should be reported as an SAE

Comments:

The term severe is often used to describe the intensity (severity) of a specific event. This is not the same as serious, which is based on patients/event outcome or action criteria.

* Life threatening in the definition of an SAE refers to an event in which the patient was at risk of death at the time of the event; it does not refer to an event that hypothetically might have caused death if it were more severe.

**Hospitalisation is defined as an unplanned, formal inpatient admission, even if the hospitalisation is a precautionary measure for continued observation. Thus hospitalisation for protocol treatment (e.g. line insertion), elective procedures (unless brought forward because of worsening symptoms) or for social reasons (e.g. respite care) are not regarded as an SAE.

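### AEs outside CTCAE are graded on a scale that stops at 3 (severe), while the SAE Form and the AE outcome definition call for CTCAE v4.0 grades, and nothing links the two scales

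*Protocol*

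**What the plan says.** Protocol 10.3.1.1 sets CTCAE v4.0 as the general standard for reviewing AEs. It then gives a separate rule for events that CTCAE does not list: the investigator grades them, and they are "recorded on the AE Form using a scale of (1) mild, (2) moderate or (3) severe". The same section sends a serious event to both forms: "AEs should be reported on an AE Form (and where applicable on an SAE Form").

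Protocol 10.3.1.2, on the SAE Form, asks the investigator for causality and for "the severity of the AE which should be documented using the CTCAE version 4.0". It makes no exception for unlisted events. Appendix 4 includes "Is life-threatening" among the criteria for a serious event, as well as death unrelated to the original cancer.

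Protocol 15.2 defines the AE outcome "with grade of events recorded by CTCAE version 4.0" and compares treatments on the number of patients with at least one grade 3 or grade 4 event. Appendix 5 also names CTCAE v4.0 for recording toxicities. Protocol 15.4 promises the table: "AEs, as a whole, will be reported as the number of patients on each treatment arm experiencing each event at each grade".

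**The concern.** The scale for unlisted events is closed and has no level above severe. Elsewhere the protocol treats grade 4 as a level of its own (1.4, 6.2, 15.2). An unlisted event worse than severe thus falls under two instructions that cannot both be met with one grade: a ceiling of 3 on the AE Form and a CTCAE grade on the SAE Form.

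This bears on a declared outcome. Section 3.3 lists adverse events, as defined by Section 10.0, as a secondary outcome, and Section 10.0 contains the three-point rule. Section 15.2 describes the same outcome as graded by CTCAE. At stake are the top rows of the by-grade safety table, the reconciliation of AE and SAE records for the same event, and a consistent treatment of fatal events.

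**Working it through.** There is no stated figure to reproduce and no sample-size or power arithmetic is involved. The check is to follow one unlisted event through the rules as written.

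**Inputs**

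- AE Form scale for unlisted events: 1, 2 or 3 (10.3.1.1).
- SAE Form scale: CTCAE v4.0, no exception (10.3.1.2).
- Outcome scale: CTCAE v4.0, no exception (15.2, Appendix 5).
- Levels above 3: grade 4 is used in 1.4, 6.2 and 15.2. The protocol does not print a grade 5; I assume that a fatal event is grade 5.
- Serious by definition: life-threatening events, and deaths unrelated to the original cancer (Appendix 4). Under 10.4, the AE behind a death not clearly due to progression must be reported as an SAE.

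**Mapping of an unlisted event**

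| True severity | Highest AE Form entry | Grade on CTCAE levels | Difference |
|---|---|---|---|
| Mild | 1 | 1 | 0 |
| Moderate | 2 | 2 | 0 |
| Severe | 3 | 3 | 0 |
| Life-threatening | 3 | 4 | 4 − 3 = 1 |
| Fatal | 3 | 5 (assumed) | 5 − 3 = 2 |

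The scales agree for the first three levels and part only in the last two rows. Those are the rows in which the event is also an SAE and a second grade is requested.

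**Effect on the outputs**

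1. *By-grade table (15.4).* If the AE Form supplies the grade, these events sit in the grade 3 row, which is too high, and the rows above it are too low. If the SAE Form supplies the grade for serious events, the table need not be affected. The protocol does not say which.
2. *At least one grade 3 or grade 4 event (15.2, 15.4).* A patient with a life-threatening unlisted event counts once whether it is coded 3 or 4, so the result is unchanged.
3. *The same comparison for a fatal unlisted event.* Coded 3, it counts. Coded 5, it does not count on a literal reading of grade 3 or grade 4. A fatal event that CTCAE lists would also fall outside that literal count, so as written listed and unlisted fatal events are treated differently.

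**Frequency.** The documents give no figure for how many AEs fall outside CTCAE, or how many of those would be life-threatening or fatal. Zero is possible.

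**The case against.** Section 10.3.1.1 states a general rule and then a specific exception, and general statements in 15.2 and Appendix 5 need not contradict an exception made elsewhere. Appendix 4 separates severity from seriousness, so a mild, moderate, severe intensity scale, with danger to life and death captured on other forms, is a coherent design. Section 10.3.1.2 also refers sites to SAE Form guidelines that are not shown and might resolve the matter.

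Part of this stands. It lowers the importance of the point and rules out saying that the two forms must always disagree. It does not remove the gap. The SAE instruction calls for a CTCAE severity for every SAE, and the analysis sections speak of one set of grades. Nowhere does the protocol say how a three-level grade enters that set. If no event ever falls outside CTCAE, the sentence is idle; if some do, its scale is too short.

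Three stronger readings are tempting, and the documents do not support them:

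- *That the analysis tables will carry the capped value.* No section says that the AE Form supplies the grade in 15.4. A statistical analysis plan could take it from the SAE Form for serious events.
- *That unlisted events are the ones most likely to be new or unexpected for olaparib.* Expectedness is judged against the Investigator Brochure or product information (10.3.2, Appendix 4), not against CTCAE. A listed event can be unexpected.
- *That safety oversight is weakened.* SAE reporting within 24 hours, independent review of seriousness and causality, SUSAR reporting, DMC review of SAEs and the Death Form do not depend on the AE Form grade (10.3.1.2 to 10.4).

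**Conclusion.** The point holds as a minor inconsistency in a stated rule. Followed as written, 10.3.1.1 prevents an unlisted life-threatening or fatal event from being graded above 3 on the AE Form, whereas 10.3.1.2, 15.2 and Appendix 5 ask for CTCAE v4.0 grades without exception. No section connects the scales or chooses between the forms.

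For each such event the shortfall is one grade if life-threatening and two if fatal, the latter on the assumption that fatal is grade 5. It reaches the 15.4 table only if the AE Form grade is the one used. The number of events is unknown and may be zero. The primary analysis is not touched, the grade 3 or 4 comparison does not move for life-threatening events, and there is no ground for suggesting bias between arms.

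**What to change.** In 10.3.1.1, grade unlisted AEs on the same levels as CTCAE by adding (4) life-threatening and (5) fatal. Require the same grade on the AE Form and the SAE Form when an event is entered on both.

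The change has one side effect that must be dealt with at the same time. A fatal unlisted event coded 5 would leave a literal grade 3 or grade 4 count, as a listed fatal event would. Sections 15.2 and 15.4 should therefore either count patients with an event of grade 3 or higher, or keep the present count and report fatal AEs separately.

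The cost is one line in 10.3.1.1, two codes on the AE Form and a short edit in 15.2 and 15.4. Section 11.1 already allows CRFs to be amended during the trial. No treatment rule changes.

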10.3.1.2 Serious Adverse Events

For more detailed instructions on SAE reporting refer to the SAE Form Completion Guidelines contained in section 5.0 of the ISF.

AEs defined as serious and which require reporting as an SAE should be reported on an SAE Form. When completing the form, the Investigator will be asked to define the causality and the severity of the AE which should be documented using the CTCAE version 4.0.

On becoming aware that a patient has experienced an SAE, the Investigator (or delegate) must complete, date and sign an SAE Form. The form should be faxed together with a SAE Fax Cover Sheet to the Trial Office using one of the numbers listed below as soon as possible and no later than 24 hours after first becoming aware of the event:

To report an SAE, fax the SAE Form with an SAE Fax Cover Sheet to:

[name] or [name]

On receipt the STOMP Trial Office will allocate each SAE a unique reference number. This number will be transcribed onto the SAE Fax Cover Sheet which will then be faxed back to the site as proof of receipt. If confirmation of receipt is not received within 1 working day please contact the Trial Office. The SAE reference number should be quoted on all correspondence and follow-up reports regarding the SAE. The SAE Fax Cover Sheet completed by the Trial Office should be filed with the SAE Form in the ISF.

For SAE Forms completed by someone other than the Investigator the Investigator will be required to countersign the original SAE Form to confirm agreement with the causality and severity assessments. The form should then be returned to the Trial Office in the post and a copy kept in the ISF.

Investigators should also report SAEs to their own Trust in accordance with local practice.

10.3.1.3 Provision of Follow-up Information

Patients should be followed up until resolution or stabilisation of the event. Follow-up information should be provided on a new SAE Form (refer to the SAE Form Completion Guidelines for further information).

STOMP Protocol

10.3.2 Trial Office

On receipt of an SAE Form seriousness and causality will be determined independently by a Clinical Coordinator. An SAE judged by the Investigator or Clinical Coordinator to have a reasonable causal relationship with the trial medication will be regarded as a Serious Adverse Reaction (SAR). The Clinical Coordinator will also assess all SARs for expectedness. If the event meets the definition of a SAR that is unexpected (i.e. is not defined in the Investigator Brochure) it will be classified as a Suspected Unexpected Serious Adverse Reaction (SUSAR).

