1.4 Olaparib

Olaparib (AZD2281, KU-0059436, KuDOS/AstraZeneca) is a PARP inhibitor in development for the treatment of patients who have cancers associated with genetic BRCA mutations and in patients with deficiency in DNA repair, specifically homologous recombination repair deficiency. Clinical study data to date in patients with advanced cancer have shown olaparib to have significant anti-tumour activity as a single agent in ovarian and breast cancer patients with known homologous recombination deficiency: BRCA1^{-/-} or BRCA2^{-/-} (Audeh *et al.*, 2010; Fong *et al.*, 2009; Tutt *et al.*, 2010). Due to the molecular targeting of olaparib to specific subsets of tumours and sparing of normal cells, this has raised the opportunity for relatively less toxic cancer monotherapy using such a PARP 1 inhibitor compared with conventional treatments, such as chemotherapy.

Olaparib has been tested in a standard range of safety pharmacology studies e.g. dog cardiovascular and respiratory function tests, and the rat Irwin test. There were no noticeable effects on the cardiovascular or respiratory parameters in the anaesthetised dog

STOMP Protocol

or any behavioural, autonomic or motor effects in the rat at the doses studied. The toxicology studies indicate that the target organ of toxicity is the bone marrow. Further information can be found in the current version of the olaparib Investigator's Brochure.

More than 950 patients have now received olaparib either as monotherapy (11 studies) or in combination with other chemotherapy agents. Data from these studies indicate that olaparib is generally well tolerated as monotherapy at doses up to 400 mg bd capsules in patients with solid tumours. Administration of olaparib has been associated with:

- Anaemia, generally mild to moderate (National Cancer Institute Common Terminology Criteria for Adverse Events [CTCAE] grade 1-2)
- Neutropenia, predominantly mild to moderate (CTCAE grade 1-2)
- Thrombocytopenia, generally mild to moderate (CTCAE grade 1-2), sometimes severe (CTCAE grade 3-4)
- Pneumonitis events with no consistent clinical pattern have been reported in a small number of patients
- Nausea and vomiting, generally mild to moderate (CTCAE grade 1-2), intermittent and manageable on continued treatment
- Fatigue, generally intermittent and of mild to moderate intensity (CTCAE grade 1-2)

For further information please refer to the current version of the olaparib Investigator's Brochure.

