10.3.2.1 Reporting to the Competent Authority and Research Ethics Committee

Suspected Unexpected Serious Adverse Reactions

The Trials Office will report a minimal data set of all individual events categorised as a fatal or life threatening SUSAR to the Medicines and Healthcare products Regulatory Agency (MHRA and Research Ethics Committee (REC) within 7 days. Detailed follow-up information will be provided within an additional 8 days.

All other events categorised as SUSARs will be reported within 15 days.

Serious Adverse Reactions

The Trial Office will report details of all SARs (including SUSARs) to the MHRA and REC annually from the date of the Clinical Trial Authorisation, in the form of an Annual Safety Report.

Adverse Events

Details of all AEs will be reported to the MHRA on request.

Other Safety Issues Identified During the Course of the Trial

The MHRA and REC will be notified immediately if a significant safety issue is identified during the course of the trial.

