*** Medical judgment should be exercised in deciding whether an AE is serious in other situations. Important AEs that are not immediately life threatening or do not result in death or hospitalisation but may jeopardise the subject or may require intervention to prevent one of the other outcomes listed in the definition above, should be considered serious.

Serious Adverse Reaction

An AR which also meets the definition of a SAE.

STOMP Protocol

Suspected Unexpected Serious Adverse Reaction

A SAR that is unexpected i.e. the nature, or severity of the event is not consistent with the applicable product information.

A SUSAR should meet the definition of an AR, UAR and SAR.

Unexpected Adverse Reaction

An AR, the nature or severity of which is not consistent with the applicable product information (e.g. Investigator Brochure for an unapproved IMP or (compendium of) Summary of Product Characteristics (SPC) for a licensed product).

When the outcome of an AR is not consistent with the applicable product information the AR should be considered unexpected.

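### Section 10.3.2 reduces expectedness to whether a reaction is in the Investigator Brochure and omits Appendix 4's severity and outcome criteria, so a SUSAR could miss its 7- or 15-day report

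*Protocol*

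**What the plan says.** The protocol explains what makes a serious reaction unexpected in two places.

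- **Section 10.3.2 (Trial Office)** assigns the task: "The Clinical Coordinator will also assess all SARs for expectedness". The rule follows directly: "If the event meets the definition of a SAR that is unexpected (i.e. is not defined in the Investigator Brochure"), in which case the event becomes a SUSAR.
- **Appendix 4** defines a SUSAR as "A SAR that is unexpected i.e. the nature, or severity of the event is not consistent with the applicable product information". Under the unexpected adverse reaction entry it adds: "When the outcome of an AR is not consistent with the applicable product information the AR should be considered unexpected". It also says that a SUSAR has to satisfy the unexpected adverse reaction definition, so the outcome criterion carries over to SUSARs.

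Section 10.0 opens by pointing the reader to Appendix 4 for definitions.

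Section 10.3.2.1 ties the reporting clock to the classification. The Trial Office reports anything "categorised as a fatal or life threatening SUSAR to the Medicines and Healthcare products Regulatory Agency (MHRA and Research Ethics Committee (REC) within 7 days". For the remainder, "All other events categorised as SUSARs will be reported within 15 days". For SARs in general, "The Trial Office will report details of all SARs (including SUSARs) to the MHRA and REC annually". Section 10.3.2.2 sends every SUSAR, and any other safety issue that arises, to Principal Investigators.

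**The concern.** The parenthesis in Section 10.3.2 begins with 'i.e.', so it presents itself as the meaning of 'unexpected' and not as an example. What it states is a listing test, with no mention of severity or outcome. Appendix 4 includes both.

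The two texts can therefore classify the same event differently. This matters because expectedness decides whether a SAR goes to the MHRA and REC as an individual report within days or, absent another trigger, in a yearly summary. It also decides whether Principal Investigators are told as a matter of course. The cases on which the texts part are known reactions that turn out worse than the Brochure describes, and the severity and outcome criteria exist to catch exactly these.

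**Working it through.** No arithmetic applies. The check sets the two rules side by side, runs each kind of SAR through both, and then follows the reporting consequence. The Investigator Brochure is taken as the reference document under both rules.

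**Step 1: classification**

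| Serious adverse reaction | Section 10.3.2, read literally | Appendix 4 |
|---|---|---|
| Not in the Brochure | Unexpected | Unexpected |
| In the Brochure; severity and outcome consistent with it | Expected | Expected |
| In the Brochure; severity not consistent with it | Expected | Unexpected |
| In the Brochure; outcome not consistent with it | Expected | Unexpected |

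The rules agree on the first two rows and disagree on the last two. With the Brochure as the common reference, the disagreement runs one way only: the literal Section 10.3.2 rule can miss a SUSAR that Appendix 4 would catch, but cannot add one.

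**Step 2: consequence for the last two rows**

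| Recipient | If classed as a SUSAR | If classed as expected |
|---|---|---|
| MHRA and REC, individual report (10.3.2.1) | 7 days if fatal or life-threatening; otherwise 15 days | None by this route |
| MHRA and REC, annual report (10.3.2.1) | Yes | Yes |
| MHRA and REC, significant safety issue (10.3.2.1) | Immediately, if so judged | Immediately, if so judged |
| Principal Investigators (10.3.2.2) | Yes, as a SUSAR | Only if it counts as another safety issue |
| DMC (10.3.2.3) | Yes, with all SAEs | Yes, with all SAEs |
| Manufacturer (10.3.2.4) | Within 24 hours | Within 24 hours |

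Misclassification removes two things: the individual report on the 7- or 15-day clock, and the automatic notice to Principal Investigators. The other four routes do not depend on expectedness.

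**Step 3: can such events reach this decision?** Yes. Section 10.3.1.2 has the investigator grade severity on the SAE Form. Section 10.4 requires deaths not clearly due to progression to enter as SAEs. The Coordinator therefore has the severity and outcome in hand, but the wording of Section 10.3.2 gives them no role in judging expectedness.

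**Step 4: can particular reactions be named?** Not from the protocol. Section 1.4 summarises the known effects and refers to the Brochure for the rest. It describes anaemia as generally, and neutropenia as predominantly, grade 1-2, and thrombocytopenia as sometimes grade 3-4. On pneumonitis it says: "Pneumonitis events with no consistent clinical pattern have been reported in a small number of patients", with no grade or outcome. These entries show the kind of reaction for which severity or outcome could matter. They do not establish what the Brochure lists.

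**The case against.** The best defence is that Section 10.3.2 sets up no second test. It speaks of meeting a definition, Section 10.0 says that the definitions are in Appendix 4, and the parenthesis can be read as shorthand. 'Not defined in the Brochure' might even be stretched to cover a severity that the Brochure does not describe. A careful Coordinator could therefore apply the wider test. This stands as a reason to say that a case could be missed and not that it will be. It does not remove the conflict, because the parenthesis sits at the point of decision and restates the definition more narrowly.

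Two stronger readings are tempting, and the protocol supports neither.

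- A reader might infer that a fatal pneumonitis or a life-threatening neutropenia would be misclassified. That would require knowing that the Brochure lists the reaction and that the severity or outcome is inconsistent with its text. The Brochure is not at hand, and Section 1.4 cannot stand in for it: 'generally' and 'predominantly' do not exclude severe cases, and pneumonitis carries no grade at all.
- A reader might infer that a SAR classed as expected reaches the authorities only through the annual report, so that each such case waits up to 12 months. Section 10.3.2.1 also requires immediate notification of a significant safety issue, and DMC review and the 24-hour report to the manufacturer cover all SAEs. Waiting for the annual report is the worst case under the literal rule, not the expected course. These safeguards still do not replace the individual SUSAR report.

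**Conclusion.** The point holds as an internal inconsistency. Section 10.3.2 states a narrower test of expectedness than Appendix 4, and the difference can only lead to SUSARs being under-recognised.

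For an affected case, the loss is the 7-day report (fatal or life-threatening) or 15-day report (other) to the MHRA and REC, together with the SUSAR notice to Principal Investigators. The case remains visible to the DMC and the manufacturer and appears in the annual report.

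The conclusion assumes that the Coordinator follows the parenthesis literally and that the Brochure is the reference document. The number and type of reactions affected cannot be estimated without the Brochure; there may be none or several. The textual mismatch itself depends on neither the Brochure nor any analysis plan. The change should be made because it is cheap and bears directly on expedited safety reporting.

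**What to change.** In Section 10.3.2, replace the parenthesis with the Appendix 4 test: a SAR is unexpected if its nature, severity or outcome is not consistent with the current Investigator Brochure, which serves as the reference safety information. Keeping the Brochure named is useful, because Appendix 4 speaks more generally of product information and mentions both a Brochure and an SPC as examples.

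Then recheck the SARs already classed as expected against the severity and outcome criteria, and report any that prove to be SUSARs.

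The cost is one line in an amendment, one pass through the existing SARs, and possibly a few more expedited reports. No dose, treatment rule or analysis changes.
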